ACTG NETWORK COORDINATING CENTER
Social & Scientific Systems, Inc., a DLH Holdings Company
[name]
[name] [name]
[contact]

LETTER OF AMENDMENT #1

DATE: June 22, 2023
TO: ACTG CTU Principal Investigators, CRS Leaders, and CTU/CRS Coordinators
FROM: A5362 Protocol Team
SUBJECT: Letter of Amendment #1 for Protocol A5362, Version 2.0

The following information affects the A5362 study and must be forwarded to your institutional review board (IRB)/ethics committee (EC) as soon as possible for their information and review. This Letter of Amendment (LOA) should be implemented immediately, prior to IRB/EC approval, to eliminate immediate hazard to participants.

The following information also affects the Sample Informed Consent (SIC). A letter informing participants about the contents of this LOA and an addendum to the SIC were provided electronically to sites on 16Jun2023.

Sites should implement the LOA immediately and inform IRB/EC and any other applicable regulatory entities of the LOA. Sites are still required to submit an LOA registration packet to the DAIDS Protocol Registration Office (PRO) at the Regulatory Support Center (RSC). Sites will receive a registration notification for the LOA once the DAIDS PRO verifies that all required LOA registration documents have been received and are complete. An LOA registration notification from the DAIDS PRO is not required prior to implementing the LOA. A copy of the LOA registration notification, along with this letter and any IRB/EC correspondence, should be retained in the site's regulatory file.

In April 2023, the study temporarily closed to screening and accrual due to an unanticipated trend in outcome events, which triggered review by the National Institute of Allergy and Infectious Diseases (NIAID) Therapeutic and Prevention Data and Safety Monitoring Board (DSMB), which met on 01Jun2023 to review all available safety and efficacy data from A5362. The DSMB recommended that A5362 permanently close to accrual because of the high rate of treatment failure and TB recurrence. There were no other safety concerns related to study regimen. The A5362 team, NIAID and DAIDS leadership, and ACTG leadership concur with the following DSMB recommendations for implementation:

- Permanently close A5362 to accrual.

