## **2.3 Study Objectives**

This Primary SAP addresses the following primary and secondary objectives listed in the study protocol. We address other study objectives outlined in the protocol in subsequent secondary analysis plans.

We will analyze the primary efficacy objective below (2.3.1.1) using a superiority framework based on a one-sided 0.05 alpha level test. For analyses of other objectives, we will present estimates of the parameter of interest alongside their respective two-sided confidence intervals, as specified in Section 5.

We will finalize all analyses for the primary analysis report once the last enrolled participant has completed the week 26 study visit and all queries have been resolved.

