### 2.3.2 Secondary Objectives

Each is a comparison between Arm 1 and Arm 2 unless otherwise specified.

- 2.3.2.1 To compare proportion of participants who experience a favorable composite efficacy outcome at 65 weeks between Arm 1 and Arm 2 participants
- 2.3.2.2 To compare premature regimen discontinuation (tolerability) between Arm 1 and Arm 2 participants
- 2.3.2.3 To estimate and compare CFZ-associated increases in QT interval (QTcF, using the Fridericia correction)
- 2.3.2.4 To estimate and compare time to stable liquid and solid mycobacterial culture conversion
- 2.3.2.5 To compare proportion of participants with liquid and solid culture conversion at weeks 8 and 12 between Arm 1 and Arm 2 participants
- 2.3.2.6 To compare days to positivity in automated liquid mycobacterial culture over treatment time
- 2.3.2.7 To compare chest radiographic score (with specific attention to resolution of cavitary disease) between Arms from baseline to end of treatment (Arm 1, week 13; Arm 2, week 26) between Arm 1 and Arm 2 participants
- 2.3.2.8 To compare proportions of participants who experience a favorable clinical/bacteriologic treatment outcome at 65 weeks between Arm 1 and Arm 2 participants
- 2.3.2.9 To estimate cumulative relapse and recurrence proportions up to week 65 for participants on Arm 1 and Arm 2
- 2.3.2.10 To determine CFZ pharmacokinetic (PK) parameters in plasma in Arm 1
- 2.3.2.11 To compare PK parameters when CFZ is given with a loading dose in Arm 1 and without a loading dose in Arm C
- 2.3.2.12 To objectively and subjectively assess CFZ-associated skin hyperpigmentation between Arm 1 and Arm 2 participants

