## 2.4 Overview of Sample Size Considerations

We plan to enroll a total of 185 participants; approximately 110 in Arm 1, 55 in Arm 2, and 20 in Arm C. We estimate that we will have at least 90% power to detect an effect between Arm 1 and Arm 2 with respect to the primary efficacy outcome. We assume 70% culture conversion by week 12 in Arm 2 and a hazard ratio of 1.8. We use a 2:1 allocation ratio and assume that 10% of participants will have unevaluable culture conversion results.

For the primary safety outcome, we will compare proportions of participants with any Grade 3 or higher adverse events (AE) between Arms. Table 10.4-2 from the study protocol (copied below) gives the power we would have to detect that Arm 1 is inferior to Arm 2 assuming a two-sided type 1 error of 0.10, 10% probability of developing an AE in the SOC Arm, and varying probabilities (15-30%) of developing an AE in experimental Arm. We also provide the 90% confidence interval (CI) width for the comparison.

Protocol Table 10.4-2

Power	N1	N2	N	Arm 1 Proportion with $\ge$ Grade 3 AE	Arm 2 Proportion with $\ge$ Grade 3 AE	Two-sided type 1 error	90% CI Width
0.13	100	50	150	0.15	0.10	0.10	0.210
0.36	100	50	150	0.20	0.10	0.10	0.218
0.64	100	50	150	0.25	0.10	0.10	0.225
0.85	100	50	150	0.30	0.10	0.10	0.230

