#### 4.1.1 Analysis set definitions

##### 4.1.1.1 Analysis sets (used for primary (5.1.1) and key secondary (5.1.2) estimands):

- **Efficacy Set:**  
All participants who are randomized to study treatment and are not late exclusions.  
(Participants will be late exclusions if they do not have any positive culture (liquid or solid) at screening, entry, or week 1, or if they have TB that is RIF-resistant or INH-resistant identified at screening or entry.)
- **Safety Set:**  
All participants who start assigned study treatment.
- **Start treatment/not late exclusion set:**  
All participants who start assigned study treatment and are not late exclusions.
- **Alive/adequate treatment set:**  
All participants who complete an adequate course of treatment as defined within Sections 10.2.5 and 10.2.6 of the protocol and who do not die during treatment.
- **Per protocol Set:**  
All participants who start and complete assigned study treatment.

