#### 5.1.3.2 QT Prolongation (Objective 2.3.2.3; Outcome Measures 3.2.3.1, 3.2.3.2, 3.2.3.3)

We will compare the mean change in QTcF from screening to weeks 2, 8, and 13 (3.2.3.1) between Arm 1 and Arm 2 in the safety set using a GEE model with exchangeable correlation structure and time by treatment interaction terms (treating time as a categorical variable).

We will compare the change from baseline in QTcF over time between arms using a linear mixed effects model. Randomization arm and week (time) will be fixed effects and participant ID will be a random effect.

We will compare the odds of participants having maximum occurrence of absolute QTcF  $\geq 480$  ms and  $<500$  ms, or  $\geq 500$  ms (3.2.3.2) between Arm 1 and Arm 2 in the safety set using a proportional odds model, if the proportional odds assumption is satisfied. We will assess the proportional odds assumption using the score test for the proportional odds assumption implemented in SAS PROC LOGISTIC. If the score test indicates a statistically significant result at the 0.05 level, we will also assess the proportional odds assumption graphically to confirm. If graphical evidence suggests the proportional odds model is valid, we will use it for analysis.

If the proportional odds assumption does not hold, we will instead estimate the difference in binomial proportions and 95% confidence intervals for the collapsed category of QTcF  $\geq 480$  ms (including QTcF  $\geq 500$  ms), and separately for the category QTcF  $\geq 500$  ms.

The analysis of outcome measure 3.2.3.3 will follow the same approach as that of 3.2.3.2.

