**5.1.3.11 CFZ-associated skin hyperpigmentation (Objective 2.3.2.12; Outcome Measures 3.2.12 and 3.2.13)**

We will compute the total color difference scores using the CIELAB color space output values, (L, a, b), from the colorimeter device. Since each reading is done in triplicate, we will use the average scores from the three readings for L, A, and b for each participant. The analysis for each anatomical locations will be separate.

The CIE76 formula for total color difference, Delta E, is given by:  $\Delta E = \sqrt{\Delta L^2 + \Delta a^2 + \Delta b^2}$

We will compare the mean change in total color difference ( $\Delta E$ ) from week 0 (entry) to each of weeks 8, 13, 26, 65 in Arm 1 vs Arm 2 at each of the following locations; (1) forehead, (2) left cheek, (3) right cheek, (4) chin in the mITT-B population. That is, for each anatomical location, we will compute the difference between  $\Delta E$  at week 0 and week 8 for each of Arm 1 and Arm 2. We will compare the differences with a t-test.

We will also compare the mean change in total color difference ( $\Delta E$ ) from week 0 (entry) to each of weeks 8, 13, 26, 65 in Arm 1 vs Arm 2 using, for each participant in the safety set, the location with the maximum change. We will compare differences between arms with a t-test.

We will compare the 'mean change in coloration score' and 'mean distress related to skin coloration score' for Arm 1 vs Arm 2 at each of weeks 0, 8, 13, 26, and 65 in the safety set.

Using subjective assessments of clinical images, we will compare the proportion of participants with each degree of skin discoloration in Arm 1 vs Arm 2 in the safety set. We will provide the point estimates together with the Pearson Klopper exact 95% confidence intervals.

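### Image-graded skin discoloration is to be compared between arms, but the SAP specifies only one-sample intervals for each degree, so no between-arm effect is estimated and the order of the degrees is not used

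*SAP*

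**What the plan says.** Secondary objective 2.3.2.12 is "To objectively and subjectively assess CFZ-associated skin hyperpigmentation between Arm 1 and Arm 2 participants". SAP 5.1.3.11 covers it with colorimeter readings, two self-reported scores and, in its last paragraph, graded clinical images. For the images the plan is that "we will compare the proportion of participants with each degree of skin discoloration in Arm 1 vs Arm 2 in the safety set". The method follows: "We will provide the point estimates together with the Pearson Klopper exact 95% confidence intervals".

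Three other places bear on this.

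- SAP 2.3 sets the inferential frame for everything except primary efficacy: "For analyses of other objectives, we will present estimates of the parameter of interest alongside their respective two-sided confidence intervals". No alpha, test or power is attached to the image grades.
- SAP 5.1.3.2 analyses another set of ordered categories, QTcF bands, "using a proportional odds model, if the proportional odds assumption is satisfied". Its fallback is a difference in proportions for collapsed categories.
- SAP 4.1.3.1 uses the same exact interval for a single proportion in Arm 1 alone.

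The documents supplied do not give the image scale, its number of degrees, or the visits at which images are graded.

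**The concern.** There are two linked gaps.

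First, the sentence promises a comparison but names no between-arm quantity. A Clopper-Pearson interval belongs to one binomial proportion. Two of them side by side are not an estimate of a difference, a ratio or an odds ratio. For other categorical outcomes the SAP does name such a measure: a difference in proportions in 5.1.3.1 and 5.1.3.4, and an odds ratio in 5.1.3.2.

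Second, degrees of discoloration are naturally read as ordered, and the plan treats them as unrelated categories. When a whole distribution moves towards darker degrees, participants both enter and leave the middle degrees. A middle degree can then show no difference, or a lower proportion in Arm 1, although Arm 1 is worse at every cut-point.

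At stake is whether the image item gives one readable answer on how much more Arm 1 discolors, or a set of pairs from which each reader must form a judgement.

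**Working it through.** **No figure to reproduce.** The SAP states no sample size, power or effect size for the image grades, so everything below is illustrative.

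**Inputs from the documents.** Planned allocation is "approximately 110 in Arm 1, 55 in Arm 2, and 20 in Arm C" (SAP 2.4). The analysis set is the safety set, defined as "All participants who start assigned study treatment" (SAP 4.1.1.1). The Letter of Amendment reports the recommendation "Permanently close A5362 to accrual", and the final number enrolled is not given.

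**Assumed inputs.** Four ordered degrees, several Arm 2 distributions, and a common odds ratio of 2.5 at every cut-point. Sizes are 100 v 50 and 110 v 55, with 55 v 28 as a half-size case.

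**Step 1: a middle degree can mislead.** Take Arm 2 at 40/30/20/10% from lightest to darkest. The proportions at or above degrees 2, 3 and 4 are 0.60, 0.30 and 0.10, with odds 1.500, 0.429 and 0.111. Multiplying by 2.5 gives odds 3.750, 1.071 and 0.278, so Arm 1 has 0.789, 0.517 and 0.217 at or above those degrees. Differencing gives Arm 1 at about 21.1/27.2/30.0/21.7%.

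Arm 1 is worse at every cut-point (0.789 v 0.60, 0.517 v 0.30, 0.217 v 0.10). Yet degree 2 is less frequent in Arm 1 (27.2% v 30%). The four differences, in points, are about -18.9, -2.8, +10.0 and +11.7.

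**Step 2: what one ordinal estimate would say.** With the same distributions, the probability that an Arm 1 participant has a darker degree than an Arm 2 participant, counting ties as half, is:

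- Arm 1 darker: 0.272×0.40 + 0.300×0.70 + 0.217×0.90 = 0.514
- Tied: 0.211×0.40 + 0.272×0.30 + 0.300×0.20 + 0.217×0.10 = 0.248
- Total: 0.514 + 0.248/2 = 0.638

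No difference would be 0.5. The equivalent summary on the model scale is the common odds ratio, 2.5.

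**Step 3: how much information the order carries.** Simulated power at two-sided 5% is shown for a tie-corrected Wilcoxon test, which is the score test of the proportional odds model, and for a Fisher test in the single best degree. There were 1,500 replicates per row at 100 v 50 and 2,500 at 110 v 55. At a power near 0.80 the simulation standard error is about 0.01.

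| Arm 1 v Arm 2 | Arm 2 distribution (%) | Ordinal | Best single degree | Gain (points) |
|---|---|---|---|---|
| 100 v 50 | 30/30/25/15 | 0.84 | 0.56 | 28 |
| 100 v 50 | 40/30/20/10 | 0.82 | 0.66 | 16 |
| 100 v 50 | 60/25/10/5 | 0.80 | 0.70 | 10 |
| 100 v 50 | 80/15/4/1 | 0.65 | 0.61 | 4 |
| 110 v 55 | 40/30/20/10 | 0.87 | 0.70 | 17 |
| 110 v 55 | 70/20/7/3 | 0.81 | 0.78 | 2 |
| 110 v 55 | 90/7/2/1 | 0.46 | 0.42 | 4 |

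The best single degree is known only afterwards. In the 110 v 55, 40/30/20/10 row, looking for any degree with a Bonferroni correction gives 0.61. Looking for any pair of non-overlapping Clopper-Pearson intervals, which is closest to reading the planned output by eye, gives 0.46. Looking at any degree without adjustment gives 0.83, but with a type I error of 0.14. At 55 v 28 with the same distribution, the ordinal test has 0.57 and the best single degree 0.40.

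**Step 4: where it does not help.** These cases are at 110 v 55.

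- Ten percentage points moved from the lowest to the top degree: ordinal 0.37, any degree with Bonferroni 0.48.
- A non-monotone change (Arm 1 at 40/10/40/10%): ordinal 0.20, any degree with Bonferroni 0.83.
- A very large shift (lowest degree falling from 90% to 40%): all approaches reach about 1.00.

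**The case against.** The strongest reply is that there is no test here to lose power. SAP 2.3 asks only for estimates with confidence intervals, and percentages per degree by arm with exact intervals are ordinary description. The Fisher and Wilcoxon tests above are a yardstick, not part of the plan. This stands. A reader might infer that the planned analysis is underpowered, or that it always loses power against an ordinal one. The documents support neither reading: no power is claimed, the degree distribution is unknown, and Step 4 shows cases where the per-degree view does better. Arm 2 receives no clofazimine, so a control arm mostly in the lowest degree, where the gain is only a few points, is plausible.

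A reader might also infer that objective 2.3.2.12 is left without a between-arm answer. It is not. Outcome measures 3.2.12 and 3.2.13 are the colorimetric change and the self-reported coloration and distress scores, and SAP 6.7 promises between-arm contrasts with 95% intervals for them. The image grading is in neither outcome definition nor in that list, so it is supportive.

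Two further points are fair. Detail on scale and tables may sit in the full protocol or the Analysis Implementation Plan, neither of which is available here. And a plain difference in proportions, as in SAP 5.1.3.4, would by itself supply a between-arm estimate, though it would still not use the order.

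None of this removes the gap: SAP 5.1.3.11 says the arms will be compared and names only a within-arm interval.

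**Conclusion.** The point holds in a limited form. As written, the image-grade analysis estimates no between-arm effect and does not use the order of the degrees, although the SAP uses an ordinal model for QTcF categories.

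Under a common ordered shift with odds ratio 2.5, four degrees, and 100 v 50 or 110 v 55, the ordinal comparison has about 2 to 28 points more power than the best single degree. That range rests wholly on assumed distributions. It sits at the low end when most of Arm 2 is in the lowest degree, and the advantage can reverse for non-monotone or top-degree-only effects. It also assumes that the degrees form an ordered scale, which the wording suggests but the documents do not show.

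This is a minor improvement to a supportive secondary item. No primary conclusion depends on it.

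**What to change.** In SAP 5.1.3.11, keep the percentage in each degree by arm, with the exact intervals, as description. That table is what would reveal a non-monotone or top-degree effect.

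Add one ordinal between-arm estimate with a 95% CI at each visit where images are graded. Name one measure in advance:

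- a common odds ratio from a proportional odds model, consistent with SAP 5.1.3.2; or
- the Mann-Whitney probability that an Arm 1 participant has a darker degree than an Arm 2 participant, with ties counted as half, which needs no proportional odds assumption.

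No p-value is needed, in line with SAP 2.3. If it is not already done elsewhere, the same edit can state the scale and the grading visits and list the item in SAP 6.7.

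The cost is a few words in the SAP and a line or so of code. The downside is small: an ordinal summary is less familiar than a percentage and presumes an ordered scale, which is another reason to show the percentages beside it.

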## 6 Primary Analysis Report Contents

All tables, listings, and figures provided in the final report will include totals and percentages by arm and overall unless otherwise specified. At a minimum, the final report will have the following contents.

### 6.1 Study Entry

- Accrual by site, country, and month
- Summary of late exclusions (number and reasons, by arm)
  - Participants whose screening, entry, and first post-entry visit sputum cultures all fail to grow *Mtb* complex,  
Or
  - Participants whose molecular or drug susceptibility test results demonstrate resistance to INH or RIF after enrollment

### 6.2 Baseline Characteristics

- Summary of age, sex, gender, country, Karnofsky Score (50-70, 80-100), BMI, HIV Status (stratification factor), advanced disease status determined by chest x-ray (stratification factor), Total CES Depression Scale Score, CD4 count among those HIV positive, viral load among those HIV positive
- Baseline TB diagnostic test results (AFB smear, drug susceptibility tests)
- Baseline lab results for AST, ALT, bilirubin, hemoglobin
- 2x2 table displaying concordance of site classification and central reader classification of advanced disease status by chest x-ray

### 6.3 Study Status

- Summary of off-study reasons
- Summary of participants last study visit week

### 6.4 Treatment Status

- Summary of number of participants who did not start study treatment
- Summary of extensions, changes, and restarts of study treatment
- Summary of reasons for permanently discontinuing study treatment
- Summary of number of participants who had an adequate dose of study treatment as defined in the protocol and Section 3.2.1 of this document.

### 6.5 Adverse Events

- Summary of post-entry reportable adverse events according to Section 7 of the protocol
- Summary of post-entry SAE
- Summary of QTcF at screening, weeks 2, 8, and 13
- Summary of difference in QTcF between screening, and weeks 2, 8, and 13
- Proportion with a maximum occurrence of QTcF  $\geq 480$  ms and  $< 500$  ms, and  $\geq 500$  ms

- Proportion with a maximum change from screening of QTcF  $\geq 30$  ms and  $< 60$  ms, and  $\geq 60$  ms, at any time during study treatment
- Summary of Grade 3 or higher post-entry QT prolongation adverse events

## 6.6 Primary Outcome Measures

- Kaplan-Meier curve of time to stable culture conversion in liquid media, censored at 12 weeks (outcome measure 3.1.1)
- Hazard ratio and 90% two-sided confidence interval for time to stable culture conversion in liquid media (outcome measure 3.1.1)
- Proportions in each arm, and difference in proportions with 90% confidence interval of primary safety outcome at weeks 13, 26, and 65 (outcome measure 3.1.2)

## 6.7 Secondary Outcome Measures

- Proportions in each arm, and difference in proportions with corresponding confidence interval for outcome measures 3.2.1A and B, 3.2.2, 3.2.5, 3.2.6, 3.2.9, 3.2.10.
- Contrasts that estimate the difference between mean change in QTcF scores between Arm 1 and Arm 2 from screening to weeks 2, 8, and 13 with corresponding 95% confidence intervals (outcome measure 3.2.3.1)
- Odds ratio and 95% confidence interval from proportional odds model for outcome measures 3.2.3.2 and 3.2.3.3. If proportional odds model does not hold, then difference in proportions for categories QTcF  $\geq 480$  ms and QTcF  $\geq 500$  ms between arms with corresponding 95% confidence intervals.
- Kaplan-Meier curves of time to culture conversion in liquid media, and solid media, censored at 26 weeks (outcome measure 3.2.4).
- Hazard ratio and 95% confidence intervals for time to culture conversion in liquid media, and solid media, censored at 65 weeks (outcome measure 3.2.4).
- Hazard ratio and 95% confidence intervals for time to positivity in liquid media at each time point. If proportional hazards does not hold, then we will report log-rank test. Side-by-side box plots of time to positivity (Days) at each time point (weeks 1, 2, 3, 4, 6, 8, 0, 12) (outcome measure 3.2.6)
- Estimates for changes in chest x-ray score in each arm from screening to EOT, and estimate of difference in change with 95% confidence interval (outcome measure 3.2.7)
- Contrasts that estimate the difference with corresponding 95% confidence interval between Arm 1 and Arm 2 for the change in total skin hyperpigmentation color difference from week 0 to each of weeks 8, 13, 26, and 65 at each of the following locations; (1) left cheek, (2) right cheek, (3) forehead, (4) chin, (5) using the location with the maximum change in total skin hyperpigmentation color difference. (outcome measure 3.2.12)
- Contrasts that estimate the difference in mean subjective 'change in coloration score' at each of weeks 0, 8, 13, 26, and 65 in Arm 1 vs Arm 2 with corresponding 95% confidence intervals (outcome measure 3.2.13)  
Contrasts that estimate the difference in mean subjective 'distress to skin coloration' score at each of weeks 0, 8, 13, 26, and 65 in Arm 1 vs Arm 2 with corresponding 95% confidence intervals (outcome measure 3.2.12)

